### 9.4.3 Safety Assessments

Safety evaluations include AEs, ophthalmic imaging and examinations, BCVA (ETDRS) score (assessed as both an efficacy and safety endpoint), vital signs, laboratory safety (biochemistry and haematology), [REDACTED]

AEs will be summarised in two parts: systemic events and ocular events. For systemic events, data will be displayed according to treatment received (low dose [REDACTED] vg, high dose [REDACTED] vg, and untreated). Ocular events will be displayed according to treatment allocation (including GT005 dose group) and study eye (study eye and contralateral eye).

All AEs (overall, by seriousness, by severity, by relationship) recorded throughout the study will be reported following classification according to the Medical Dictionary for Regulatory Activities (MedDRA) dictionary. [REDACTED]

Systemic safety evaluations including vital signs, laboratory safety, [REDACTED] will be summarised over time by dose and overall.

Ocular safety evaluations including ophthalmic examination variables (cataract grading, intra-ocular pressure, etc.) and BCVA scores will be summarised in the same manner as ocular efficacy variables, dependant on data type.

[REDACTED]  
[REDACTED]  
[REDACTED]  
[REDACTED]  
[REDACTED].

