### **2.7.1 Adverse events (AEs)**

Only AEs that occurred during the study period (from the date of randomization to the end of study) will be summarized. AEs recorded after screening but before the date of randomization will be listed only.

**Treatment-emergent Adverse Event (TEAE):** An adverse event is considered treatment emergent if the start date/time of the event is on or after the date of randomization, irrespective of the treatment arm. The primary summaries of AEs will be based on TEAEs.

The number (and percentage) of subjects with AEs will be summarized separately for ocular (study eye and fellow eye) and non-ocular events by treatment group in the following ways unless otherwise specified:

- Overall summary of death, subjects with any AE, any severe AE, any study treatment-related AE, any surgical procedure related AE, any AE leading to study discontinuation, any serious AE (SAE), any study treatment-related SAE, any surgical procedure related SAE, any SAE leading to study discontinuation
- AEs by primary SOC and PT
- AEs related to study treatment by SOC and PT (separately for study eye and non-ocular)
- AEs related to surgical procedure by SOC and PT (separately for study eye and non-ocular)
- SAEs by primary SOC and PT

- SAEs related to study treatment by SOC and PT (separately for study eye and non-ocular)
- SAEs related to surgical procedure by SOC and PT (separately for study eye and non-ocular)

A subject with multiple adverse events within a primary SOC is only counted once towards the total of the primary SOC.

All AEs, deaths, and SAEs (including those from the pre- and post-treatment periods) will be listed and those collected after the use of alternative GA therapies/medications, or during the pre-treatment, post-study period will be flagged. In addition, subjects who are not receiving treatment due to surgical procedure-related AEs will be listed separately by treatment group.

The MedDRA version used for reporting the AEs will be described in footnote.

For the legal requirements of ClinicalTrials.gov and EudraCT, two required tables on “on-treatment/treatment emergent” adverse events which are not serious adverse events with an incidence greater than 2% (or other cutting point as appropriate) and on “on-treatment/treatment emergent” serious adverse events and SAE suspected to be related to study treatment will be provided by system organ class and preferred term on the safety set population (i.e., the FAS of this study).

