If for the same subject, several consecutive AEs (irrespective of study treatment causality, seriousness and severity) occurred with the same SOC and PT:

[figure not shown]
- a single occurrence will be counted if there is  $\leq 1$  day gap between the end date of the preceding AE and the start date of the consecutive AE
- more than one occurrence will be counted if there is  $> 1$  day gap between the end date of the preceding AE and the start date of the consecutive AE

For occurrence, the presence of at least one SAE /SAE suspected to be related to study treatment / non-SAE has to be checked in a block e.g., among AE's in a  $\leq 1$  day gap block, if at least one SAE is occurring, then one occurrence is calculated for that SAE.

The number of deaths resulting from SAEs suspected to be related to study treatment and SAEs irrespective of study treatment relationship will be provided by SOC and PT.

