#### 5.1.1 AE date imputation

##### 5.1.1.1 Adverse event end date imputation

1. If the AE end date month is missing, the imputed end date should be set to the earliest of the (treatment follow up period date, 31DECYYYY, date of death, cut-off date if available).
2. If the AE end date day is missing, the imputed end date should be set to the earliest of the (the last visit date, last day of the month, date of death, cut-off date if available).
3. If AE year is missing or AE is ongoing, the end date will not be imputed.
4. In case the imputed AE end date is before AE start date, then use AE start date as imputed AE end date.

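### The AE occurrence rule in SAP 2.7.1 ignores which eye is affected, so overlapping events of one preferred term in different eyes count once in the registry tables

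*SAP*

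**What the plan says.** SAP 2.7.1 plans two kinds of adverse event output.

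- **General tables.** These count subjects and split them by location: "subjects with AEs will be summarized separately for ocular (study eye and fellow eye) and non-ocular events by treatment group". Further tables cover study-eye events related to treatment or to the surgical procedure. SAP 2.7.1.1 splits ocular AESIs by eye, and all AEs are listed.
- **Registry tables.** There are two, one for non-serious treatment-emergent events above an incidence threshold and one for serious events. They "will be provided by system organ class and preferred term on the safety set population". That sentence mentions no split by eye.

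The occurrence rule comes straight after the registry paragraph. It begins "If for the same subject, several consecutive AEs (irrespective of study treatment causality, seriousness and severity) occurred with the same SOC and PT". It counts one occurrence when there is at most a 1 "day gap between the end date of the preceding AE and the start date of the consecutive AE", and more than one when the gap is longer. Causality, seriousness and severity are expressly ignored. Laterality is named neither as part of the key nor as something to ignore. Within a merged block, seriousness is protected: "if at least one SAE is occurring, then one occurrence is calculated for that SAE".

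Two other places matter. On end dates, SAP 5.1.1.1 says: "If AE year is missing or AE is ongoing, the end date will not be imputed". On display, Protocol 9.4.3 says: "Ocular events will be displayed according to treatment allocation (including GT005 dose group) and study eye (study eye and contralateral eye".

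**The concern.** A preferred term does not identify an eye. Cataract, raised intraocular pressure or reduced acuity can occur in either eye under the same term. This trial makes such pairs foreseeable: subjects are at least 55 years old, the fellow eye also has AMD unless the subject is monocular, both eyes are examined, and fellow-eye events are recorded. Treatment is surgery on one eye only.

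Two events in two eyes are two occurrences by any ordinary reading. A rule keyed on subject, class and term can make them one, even when the study-eye event follows surgery and the fellow-eye event has nothing to do with it. At stake is the accuracy of the occurrence counts in two tables meant for public registries. There is also a reproducibility problem: the rule needs an end date that ongoing events do not have, so two programmers could reach different counts from the same data.

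**Working it through.** The plan states no figure on this point, so there is none to reproduce. The check has two parts.

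**1. The rule applied to five test cases.** Each case is one subject with two treatment-emergent events of the same class and term. Gap = start day of the later event minus end day of the earlier one. Events merge if the gap is 1 or less, so an overlap, which gives a negative gap, merges.

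| Case | Fellow eye | Study eye | Gap | As written | With eye in the key |
|---|---|---|---|---|---|
| A | Day 50–200, non-serious | Day 100–150, non-serious | 100 − 200 = −100 | 1 occurrence | 2 occurrences |
| B | from Day 50, ongoing | Day 100–150 | undefined | undetermined | 2 occurrences |
| C | Day 50–200, non-serious | Day 100–150, serious | −100 | 1 block, 1 SAE occurrence | 2 blocks, 1 SAE occurrence |
| D | Day 50–80 | Day 100–150 | 100 − 80 = 20 | 2 occurrences | 2 occurrences |
| E | Day 50–200, serious | Day 100–150, serious | −100 | 1 SAE occurrence | 2 SAE occurrences |

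A and E show the defect. B shows the gap in the rule for ongoing events. C shows that a serious study-eye event survives merging with a non-serious fellow-eye event. The SAP also names non-serious events in the within-block check, so a mixed pair probably adds one to each table. In every case the number of subjects affected is 1 under both versions.

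**2. An illustration of size for one preferred term.**

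From the documents:
- About 202 subjects allocated 2:1 (SAP 1.1 and 3), so 202 × 2/3 = 134.7 GT005 and 202 / 3 = 67.3 control.
- About 40% cataract extraction over 2 years after vitrectomy (Protocol 8.3), used only as an upper value.

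Assumed:
- *p*, the risk in a GT005 study eye: 20% to 40%.
- *q*, the risk in every other eye: 5% to 20%.
- Eyes are independent.
- *m*, the share of two-eye pairs that merge: 50% to 100%.

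Formulas:
- GT005: lost = 134.7 × p × q × m, out of 134.7 × (p + q) occurrences in both eyes.
- Control: lost = 67.3 × q² × m, out of 67.3 × 2q.

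Results:
- Low end (p = 0.20, q = 0.05, m = 0.5): GT005 134.7 × 0.20 × 0.05 × 0.5 = 0.7 of 33.7 (2.0%); control 67.3 × 0.0025 × 0.5 = 0.1 of 6.7 (1.2%).
- High end (p = 0.40, q = 0.20, m = 1): GT005 134.7 × 0.40 × 0.20 = 10.8 of 80.8 (13.3%); control 67.3 × 0.04 = 2.7 of 26.9 (10.0%).

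The proportional loss is pqm/(p + q) in GT005 and qm/2 in control. It is larger in GT005 whenever p exceeds q, and equal when p = q.

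Protocol 1.6.1.2 also gives a lower cataract figure, 14% of eyes after another subretinal AAV2 product. With p = 0.14, q = 0.10 and m = 1, the GT005 loss is 134.7 × 0.14 × 0.10 = 1.9.

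**The case against.** The strongest reply is that little depends on this rule. The harm summaries a reader of the study report will use count subjects and separate the eyes, and merging occurrences cannot change a count of subjects. AESI tables by eye and the listings are also untouched, and a merged block still yields its SAE. All of that stands, and it limits the point to occurrence counts in the two registry tables.

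It can also be said that the general wording on separating the eyes may govern the registry tables, in which case the merge could run within eye. The text does not settle this: that wording introduces the bulleted tables, and the registry tables come later in a paragraph of their own. A figure missing from the text of the rule, or programming specifications outside these documents, might deal with laterality. The SAP wording available does not.

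Four stronger readings are tempting, and the documents do not support them.

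- *A long-standing fellow-eye condition absorbs a new study-eye event.* The registry tables hold treatment-emergent events, which start on or after randomisation, and existing ocular conditions are recorded as medical history. If the fellow-eye event is an ongoing AE, its end date is not imputed, so the gap is undefined rather than short.
- *The registry tables understate study-eye harm.* As described, they contain no study-eye count. What is lost is an occurrence in a total over both eyes.
- *The SAP departs from Protocol 9.4.3.* The general tables do display ocular events by eye. Splitting the registry tables as well would be a preference, and nothing in the documents requires it.
- *The published comparison is biased in favour of GT005 by a known amount.* The rule applies to every arm. A larger loss in GT005 is plausible, but no source in the documents gives the share of subjects with same-term events in both eyes.

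**Conclusion.** The point holds in a narrow form. Followed as written, the rule gives a wrong occurrence count when same-term events in different eyes overlap or lie within 1 day of each other and the first has an end date. Two serious events of this kind count as one SAE occurrence. When the earlier event is ongoing, the rule gives no answer.

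The direction is plausible: surgery adds events to the study eye of GT005 subjects only, so more pairs are available to merge there. The size is unknown. The range of 0.7 to 10.8 occurrences in GT005 against 0.1 to 2.7 in control rests on assumed risks, independent eyes, an assumed merging share and the planned 202 subjects. Correlation between the eyes could raise it. Early termination, mixed pairs that lose nothing, and lower event rates would reduce it. The 40% figure is for cataract extraction, not for reported cataract events, and some subjects may have had their cataracts removed before entry. The range shows the order of size and is not an estimate for this trial.

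**What to change.** In SAP 2.7.1, apply the 1-day-gap rule within subject, SOC, PT and location, with location taken as study eye, fellow eye or non-ocular. Say explicitly that same-term events in different eyes are separate occurrences. Add a sentence on how the gap is treated when the preceding event is ongoing or otherwise lacks an end date, consistent with SAP 5.1.1.1, and confirm that overlapping events at the same location count as one. It would also help to state whether the registry tables cover both eyes together.

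The cost is one extra key in the program and a few sentences in the SAP. No new data are needed, because the other AE tables already use laterality.

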### **2.7.1.1 Adverse events of special interest / grouping of AEs**

An AESI (serious or non-serious) is one of scientific and medical concern specific to the Sponsor's product or program, for which ongoing monitoring and rapid communication by the Investigator to the Sponsor can be appropriate. AESIs should also be assessed as to whether it fits the criteria of an SAE and reported appropriately. AESI should be reported as per reporting requirements [Protocol Section 8.3].

The number and percentage of subjects with AESIs will be summarized separated for ocular (study eye and fellow eye) events by category, PT, and treatment groups. In addition, AESIs related to the study treatment and/or surgical procedure will be summarized by category, PT and treatment groups.

### 2.7.2 Deaths

All deaths will be summarized by primary SOC and PT. A listing will also be provided.

### 2.7.3 Loss in best corrected visual acuity

The number and the percentage of subjects who lost  $\geq 15/\geq 30$  letters in BCVA from baseline up to Week 96 will be presented for the study eye and the fellow eye. Missing data will not be imputed.

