#### 6.1.5 Visit 3 (Week 1) (Surgical Site)

Visit 3 (Week 1) will only apply to subjects randomised to GT005.

The following assessments will be performed:

- Concomitant medication

■ [REDACTED]

- AEs

- Vital signs

- Ophthalmic examination

- BCVA using ETDRS

- OCT macula

■ [REDACTED]

- OCT-A and/or FA if clinically indicated (if a subject converts to wet AMD)

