#### 6.1.7 Visit 4, Week 5 (Local or Surgical Site for GT005 Subjects/Telephone Call for Untreated Control Subjects)

At Week 5, subjects may choose to attend a local investigative site or surgical site for clinical assessments and ophthalmic imaging, with review of images by both the local site Investigator and the Surgeon.

Subjects allocated to untreated control will receive a telephone call from their local investigative site to review concomitant medications and AEs.

Visit 4 (Week 5) assessments listed below will only apply to subjects randomised to GT005.

The following assessments will be performed:

- Concomitant medication
- [REDACTED]
- Vital signs
- AEs
- Biochemistry/haematology
- [REDACTED]
- Ophthalmic examination
- OCT macula
- [REDACTED]
- BCVA using ETDRS
- CFP
- FAF
- OCT-A and/or FA if clinically indicated (if a subject converts to wet AMD)
- [REDACTED]
- [REDACTED]
- [REDACTED]

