#### 6.1.8 Visit 5, Week 8 (Local or Surgical Site)

Visit 5 (Week 8) assessments listed below will only apply to subjects randomised to GT005:

- Concomitant medication
- AEs
- Ophthalmic examination
- [REDACTED]
- BCVA using ETDRS
- OCT-A and/or FA if clinically indicated (if a subject converts to wet AMD)

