### 8.3 Adverse Events of Special Interest

An AESI (serious or non-serious) is one of scientific and medical concern specific to the Sponsor's product or program, for which ongoing monitoring and rapid communication by the Investigator to the Sponsor can be appropriate. AESIs should also be assessed as to whether it fits the criteria of an SAE and reported appropriately.

It is anticipated that there may be transient decreases to visual acuity related to the subretinal injection surgical procedure. A transient visual loss may be observed in the first days post-surgery due to bleb-related foveal detachment, if performed. Transient surgery-related events of decreases in visual acuity are defined as decreases occurring in close temporal association (within 24 hours) with the surgical administration of the study medication, and which are resolving at Week 1 (Visit 3) post-surgery.

Additionally, there is a known risk of cataract associated with any vitrectomy procedure. A published review from [Feng 2014] shows cataract to be common following pars plana vitrectomy with about 40% of patients requiring a cataract extraction over the following 2 years.

Transient, surgically-related decreases in visual acuity, as well as cataract will not be classified as AESI.

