### 2.7.4 Laboratory data

Laboratory parameters listed in [Table 2-1](#) will be presented graphically using boxplots of absolute change from baseline values by treatment group and visit. No summary by visit tables will be provided.

A summary table with number and percentage of subjects satisfying the criteria representing clinically relevant abnormalities defined in [Table 2-1](#) at any visit will be presented. A listing of subjects satisfying at least one criterion in [Table 2-1](#) at any visit will also be presented.

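### SAP 2.7.3 leaves its count of large BCVA losses up to Week 96 undefined; read as a loss at any visit, it sets up to nine scheduled GT005 looks against six in control

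*SAP*

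**What the plan says.** **The summary.** SAP 2.7.3 gives one subject-level count at two thresholds, at least 15 and at least 30 "letters in BCVA from baseline up to Week 96 will be presented for the study eye and the fellow eye". On missing values it says "Missing data will not be imputed". It does not state whether a loss counts at any visit, at each visit or at the last visit, whether it must be confirmed, or what the denominator is.

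**The visits.** Protocol 6.1.5, 6.1.7 and 6.1.8 each list ETDRS BCVA and restrict the visit to one arm: "Visit 3 (Week 1) will only apply to subjects randomised to GT005"; "Visit 4 (Week 5) assessments listed below will only apply to subjects randomised to GT005"; "Visit 5 (Week 8) assessments listed below will only apply to subjects randomised to GT005". Controls have only a telephone call at Week 5, and Table 2 shows their first post-baseline BCVA at Week 12. Both arms then have BCVA at Weeks 12, 24, 36, 48, 72 and 96. Protocol 7.3.10 has both eyes tested.

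**Expected early loss.** Protocol 8.3 states: "A transient visual loss may be observed in the first days post-surgery due to bleb-related foveal detachment, if performed". It describes such loss as starting within 24 hours of surgery and resolving by Week 1, and does not class it as an AESI.

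**Neighbouring text.** SAP 2.7.4 is explicit for laboratory criteria: the summary table of abnormalities "at any visit will be presented". SAP 2.6.2 (item 4.a) also plans an MMRM of BCVA change with results by visit and group, and a listing of every BCVA assessment.

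**The concern.** A subject-level count of ever crossing a threshold rises with the number of times the subject is measured. If the arms are measured unequally, their percentages differ even when the risk at each visit is the same. Protocol 5.5 names a similar assessment schedule in treated and untreated subjects as a measure against bias; for BCVA before Week 12 that does not hold.

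The two eyes differ. The fellow eye has no surgery, so extra GT005 looks there can only change ascertainment. In the study eye the early visits also pick up real loss caused by the procedure, so the count mixes two things that a reader would want apart.

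At stake is the SAP's only table of large vision loss. The study is being terminated early (SAP 1), which may leave some subjects without late visits. The early, GT005-only looks would then form a larger share of the total.

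**Working it through.** **Step 1. Count the scheduled post-baseline looks** (Protocol 6.1 for GT005, Table 2 for control).

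| Follow-up to | GT005 | Control |
|---|---|---|
| Week 12 | 4 | 1 |
| Week 24 | 5 | 2 |
| Week 48 | 7 | 4 |
| Week 96 | 9 | 6 |

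Two qualifications apply. The BCVA row of Table 1, as extracted, appears to show only Week 5 before Week 12, which would make it 7 v 6; its column alignment is damaged, so this is not firm. Protocol 4.3 offers GT005 subjects who are not dosed the control schedule (six looks), and they stay in the FAS that SAP 2.7 uses for safety.

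**Step 2. Effect of unequal looks on an any-visit count.** The documents give no rate, variance or correlation for BCVA loss, so there is no figure of the plan's to reproduce and every input below is an assumption. The per-visit risk p is the same in both arms.

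*Independent visits:* proportion = 1 − (1 − p)^k.

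| p | k = 9 | k = 7 | k = 6 | 9 v 6, points |
|---|---|---|---|---|
| 1% | 8.6% | 6.8% | 5.9% | 2.8 |
| 2% | 16.6% | 13.2% | 11.4% | 5.2 |
| 5% | 37.0% | 30.2% | 26.5% | 10.5 |
| 10% | 61.3% | 52.2% | 46.9% | 14.4 |

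The 9 v 6 ratio runs from 1.48 down to 1.31. Independence is an upper case, because acuity in one eye is strongly correlated over time.

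*Correlated visits (simulated, exchangeable correlation 0.5 to 0.8):* at p = 2%, 6.9–11.2% v 5.7–8.6%; at p = 5%, 14.6–23.4% v 12.5–18.6%. Over p = 1% to 10% the excess is 0.7 to 6.5 points and the ratio 1.14 to 1.35.

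*Steady decline plus test noise (simulated, 15-letter threshold):*

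| Mean decline | Slope SD | Test SD | 9 looks | 6 looks | Excess, points |
|---|---|---|---|---|---|
| 4 letters/year | 6 | 4 | 31.2% | 30.8% | 0.4 |
| 4 letters/year | 6 | 5 | 36.4% | 35.2% | 1.3 |
| 6 letters/year | 8 | 5 | 47.7% | 46.6% | 1.1 |

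A slower decline (3 letters per 48 weeks, slope SD 6) with test SD 5 to 6 gives 1.4 to 2.6 points. The range is therefore 0.4 to 2.6 points at 15 letters. At 30 letters the excess was about 0 in the three tabulated settings.

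**Step 3. Shortened follow-up.** If follow-up stopped at Week 24 (5 v 2 looks), independent visits give 9.6% v 4.0% at p = 2% and 22.6% v 9.8% at p = 5%. The documents do not say how many subjects are affected.

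**Step 4. Other readings.** If the summary is by visit, or at the last visit, the excess from the number of looks is 0.

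**Step 5. Laboratory table.** Biochemistry and haematology are drawn at Weeks 5, 12, 24, 48, 72 and 96 in GT005 and at Weeks 12, 24, 48, 72 and 96 in control: 6 v 5. Here the any-visit rule is written.

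**The case against.** **Any visit is inferred for BCVA.** SAP 2.7.4 writes it out and 2.7.3 does not. Protocol 9.4.3 has BCVA safety scores summarised like the efficacy variables, and SAP 2.6.2 implements several through-Week-96 endpoints by visit. This stands as a limit on the claim. However, 2.6.2 says by visit where it means that, whereas 2.7.3 gives a single count over a period. If a by-visit or last-visit summary was meant, 2.7.3 needs an edit to say so.

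**Early loss is a treatment effect.** This also stands. A reader might infer that the table is biased against GT005 by design; the documents do not support that for the study eye. Loss after subretinal surgery belongs in a safety table, and exclusion from the AESI class is not exclusion from BCVA summaries. By Protocol 8.3, and by 1.6.1.2 (structural recovery generally within one month), chiefly Week 1 falls in the expected transient window. A large loss at Week 5 or 8 is not that expected event.

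**Lasting harm would show elsewhere.** A reader might infer that lasting harm could not be told apart from transient loss. The by-visit MMRM, its plot, the BCVA listing and the ocular AE tables by eye argue against that. They do not, however, tabulate the proportion with a 15- or 30-letter loss.

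**The table is descriptive.** Protocol 9.4.2 plans no inferential testing, so no test is distorted. The percentages will still be read across arms.

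**Conclusion.** The point holds in a limited form. SAP 2.7.3 does not define its summary, and its most natural reading gives GT005 up to nine scheduled looks and control six. For the fellow eye that is purely an ascertainment difference. For the study eye it adds noise-driven crossings to real early loss.

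The size cannot be known from the documents. Under assumed steady decline it is about 0.4 to 2.6 points at 15 letters. It is larger if crossings are noisy (0.7 to 6.5 points with correlated visits and p of 1% to 10%) or if follow-up is cut short. It is smaller if Table 1 in fact has seven looks, and zero under a by-visit or last-visit reading.

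A gap of about 10 points can be produced by also assuming that 30% of GT005 subjects drop 15 letters transiently at Week 1 (42.3% v 32.6% at test SD 5). It should not be read as the artefact. The looks alone account for about 1.4 of those 9.7 points; the other 8.3 or so are surgical loss put in by assumption, at a rate that the documents do not give.

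The laboratory table has the same flaw in a smaller form (6 v 5 draws), with the any-visit rule explicit. The correction is worth making because it is cheap, not because the safety conclusions are shown to be wrong.

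**What to change.** In SAP 2.7.3:

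- Make the between-arm comparison at the visits scheduled in both arms (Weeks 12, 24, 36, 48, 72 and 96), by visit and as a loss at any common visit, with the number assessed as denominator, for each eye.
- Report GT005 losses at Weeks 1, 5 and 8 in a separate descriptive row, so that early surgical loss stays visible.
- Keep the all-visit count if wanted, labelled as based on unequal looks.
- State how unscheduled values are handled. SAP 2.1.1.4 has different rules for by-visit tables, for abnormalities and for analyses of all post-baseline values, and 2.7.3 does not say which applies.

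In SAP 2.7.4, show the GT005-only Week 5 draw separately from the any-visit comparison. Reconcile the BCVA row of Table 1 with Protocol 6.1.5, 6.1.7 and 6.1.8.

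With six looks in each arm and equal follow-up, the excess due to visit count alone is zero. The cost is SAP wording and one extra table block from data already collected. The downside is that early surgical loss is read from its own row and not from the between-arm comparison.
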